2.2 Open and Closed Fracture Study Populations

Open fracture patients and closed fracture patients represent two distinct populations within extremity fracture surgery. Open fractures are associated with wound complications that are approximately four times greater than closed fractures.^{4,5} The increased baseline risk, differing fracture treatment principles, and the distinct difference of having deep tissue exposed to micro-organisms at the time of injury provides a biologic rationale for maintaining separate open and closed fracture populations. This rationale is further strengthened by data collected from our surgeon survey that suggests many surgeons use different antiseptic skin prophylaxis procedures for open and closed fracture surgeries. Therefore, definitively comparing the effectiveness of the study solutions in each fracture population addresses distinctly different treatment decisions for surgeons. Similarly, if a difference in the effectiveness between the two study solutions were detected in only one of the fracture populations this would be an independently important clinical finding that would have an immediate effect on clinical practice.

2.3 Subgroup Objectives

The PREPARE trial will also explore the possibility of differential treatment effects of the pre-operative antiseptic skin solutions among clinically important subgroups within each independent fracture population.

2.3.1 Open Fracture Subgroups

The open fracture subgroups will be defined by i) the severity of open fracture (Gustilo-Anderson type I or II versus III);¹ ii) upper extremity versus lower extremity open fractures; iii) severity of wound contamination; and iv) presence or absence of comorbidities that affect wound healing.

2.3.2 Closed Fracture Subgroups

The closed fracture subgroups will be defined by: i) severity of soft tissue injury (Tscherne grade 3 versus grades 0-2), and ii) presence or absence of comorbidities that affect wound healing.

2.3.3 Subgroup Hypotheses

It has been established that several patient and injury factors are frequently associated with worse patient outcomes after extremity fractures.^{30,31} As a result, we hypothesize that iodine povacrylex (0.7% free iodine) in 74% isopropyl alcohol will be associated with a larger reduction in odds for SSI and unplanned fracture-related reoperations among patients with a higher risk for extremity fracture SSI. Specifically, in both the open and closed fracture populations we expect to observe this heterogeneity of treatment effect in patients with more severe soft tissue injury and patients with increased comorbidities due to the potentially broader antimicrobial coverage, stronger tissue adherence, and increased antiseptic longevity of iodine povacrylex.³² The credibility of all subgroup analyses will be assessed in accordance with criteria outlined by Sun *et al.*³³

Within the open fracture population, high-grade soft tissue injury (Gustilo-Anderson type III), lower extremity open fractures, and moderate/severe wound contamination are established predictors of SSI and reoperations from the FLOW trial.⁵ In addition, there are known differences in patients' skin flora based on anatomic region of injury. As a result, it is likely that the study interventions may be more effective in certain open fracture subgroups. Due to its broader spectrum of antimicrobial activity, the increased effectiveness observed by Swenson *et al.*, and the possible benefits observed in the FLOW trial, we hypothesize that the iodine povacrylex (0.7% free iodine) in 74% isopropyl alcohol antiseptic skin solution will be associated with a larger

reduction in odds for SSI and reoperation in open fracture patients with Gustilo-Anderson type III fractures, lower extremity fractures, and more severely contaminated wounds.

3.0 TRIAL DESIGN

3.1 Summary

This study is a multi-center pragmatic cluster randomized crossover trial with two independent populations of surgically treated fracture participants: 1) the open fracture population consisting of a minimum of 1,540 participants with open extremity fractures; and, 2) the closed fracture population of a minimum of 6,280 participants with closed lower extremity or pelvic fractures. The unit of randomization is the orthopaedic practices within clinical sites (clusters), with individual patients being the unit of analysis. The procedures for enrollment, study interventions, follow-up, and analyses within the open and closed fracture populations will follow the same protocol (with noted differences as applicable). Recruitment for each treatment group will be performed in multiple iterations of approximately two-month periods. Each orthopaedic practice will initially be randomized to use one of two pre-operative surgical skin preparation solutions (iodine povacrylex (0.7% free iodine) in 74% isopropyl alcohol versus 2% CHG in 70% isopropyl alcohol) for open and closed extremity fracture surgeries at their institution (**Figure 2**). Upon completion of the two-month period, each orthopaedic practice will crossover to the alternative treatment allocation and complete another two-month recruitment period. This process of alternating treatment periods (crossovers) will continue until the minimum sample size is achieved for each fracture population and the study's budgeted recruitment duration is completed.

Upon completion of recruitment, it is expected that each orthopaedic practice will enroll a minimum of 77 open fracture patients and 314 closed lower extremity or pelvic fracture patients per treatment (a minimum of 154 open fracture patients and 628 closed lower extremity or pelvic fracture patients in total) as applicable, and that most clinical sites will exceed this minimum recruitment goal. Clinical site personnel will screen potential patients for eligibility, and if eligible, they will be invited to participate in the trial. Study participants will be assessed at regular intervals in the one year following their fracture. The primary outcome will include any SSI event from the time of fracture to the end of the 30- and 90-day post-operative periods from their definitive fracture management surgery. The secondary outcome will include unplanned fracture-related reoperations that occur within one-year of their fracture. A blinded Adjudication Committee will review SSIs and unplanned fracture-related reoperations to confirm that they meet the criteria for being a study event.

[figure not shown]

Figure 2: Randomized Treatment Allocation, Cluster Crossover, and Recruitment

3.2 Pragmatic-Explanatory Continuum

In accordance with recommended methodology standards, we have used the PRagmatic-Explanatory Continuum Indicator Summary (PRECIS-2) toolkit to evaluate the PREPARE trial design decisions to determine whether these decisions will lead to a study that answers, “Does this intervention work under usual conditions?” (pragmatic) versus “Can this intervention work under ideal conditions?” (explanatory). The PRECIS-2 tool uses a 5-point Likert scale in 9 domains to evaluate the continuum of design choices. A domain score of 5 indicates “very pragmatic,” while a score of 1 suggests “very explanatory.” **Table 1** outlines the investigators’ assessment of the trial design and the rationale for each assessed score and **Figure 3** displays the PRECIS-2 wheel.

Table 1: PRECIS-2 Score

Domain	Score	Rationale
Eligibility	5	Eligibility criteria are very broad and include all fracture patients that would be treated in all hospital environments.
Recruitment	5	Recruitment of all consenting fracture patients treated at each participating hospital will be performed.
Setting	4	Recruitment is occurring at multiple sites across the US and Canada; however, since most of the recruiting hospitals are regional referral centers the setting is “mostly pragmatic.”
Organization	5	The interventions do not need an increase in providers or care delivery compared to the usual antiseptic care provided. For each antiseptic solution, a brief in-service training session will be provided to the clinical sites, as per any new product/procedure that is being introduced into an operating room.
Flexibility (delivery)	5	The interventions will be delivered in the usual care manner with no advice on allowed co-interventions or strict protocols to ensure compliance.
Flexibility (adherence)	-	This section is left blank according to PRECIS-2 guidance because the intervention is provided prior to patient consent and individual patient compliance is not an issue. If provider adherence is considered, the study design is rather pragmatic (4) because there will be limited encouragement to follow the manufacturer’s directions for use, other than periodic newsletters, investigator meetings, and possible provider survey during the recruitment period.
Follow-up	5	All study follow-up is consistent with usual care.
Primary outcome	5	The outcome has been validated by patients as being very relevant to the study participants and it does not require specialized expertise beyond the treating physician for diagnosis.
Primary analysis	5	All available study data will be used for analysis following the intention to treat principle.

[figure not shown]

Figure 3: PRECIS-2 Wheel

4.0 METHODS

4.1 Study Setting, Cluster Eligibility, and Selection of Clusters

This study will be coordinated by the Methods Center at the Center for Evidence-Based Orthopaedics (CEO), McMaster University, Hamilton, Ontario and by the Administrative Center within the Department of Orthopaedics at the University of Maryland School of Medicine, R Adams Cowley Shock Trauma Center, Baltimore, Maryland. Patients will be enrolled from at least 18 clinical sites in North America. Clusters (orthopaedic practices within clinical sites) will be carefully screened prior to participation in the PREPARE trial. Clinical site inclusion criteria are: 1) adequate research personnel infrastructure to manage the study; 2) adequate open fracture volume and closed lower extremity and pelvic fracture volume to complete enrollment within the study timeline (i.e., a minimum of 77 open fractures and 314 closed lower extremity fractures per year); 3) commitment from all or most orthopaedic surgeons to participate in the trial; and 4) ability to use the two alcohol-based skin preparation solutions. The exclusion criteria are: 1) lack of interest in the trial; 2) anticipated challenges with complying with the protocol; 3) conflicting studies, in the judgment of the Principal Investigators, that would inhibit patient participation; and 4) budgeting or contract constraints.

The screening process will begin with potential clinical sites completing a feasibility questionnaire that asks about research experience and infrastructure, fracture volume, current practice patterns, and interest in participating in the trial. Clinical sites that meet the eligibility criteria at this stage will be invited to participate in a series of teleconferences to review study and clinical logistics in detail with members of the study team. The Principal Investigators and study personnel will further

vet the clinical sites during these calls and will ask about hospital and patient demographics to ensure that a variety of fracture patient populations and referral patterns, ranging from large urban trauma centers to smaller referral hospitals, are included in the PREPARE trial. Study personnel will document reasons for clinical site ineligibility. Upon selection, clinical sites will be asked to complete a questionnaire that will detail current surgeon preferences and practices for pre-operative surgical preparation techniques and co-interventions known to influence the incidence of SSIs (see Section 4.7).

4.2 Eligibility Criteria

Broad eligibility criteria will be used to increase the generalizability of the trial. Potential participants will be enrolled into only one of the study populations depending on whether they meet the open or closed fracture population criteria (Section 4.2.1 or 4.2.2). Participants who meet the initial criteria for both populations will be assigned to a study population based on the criteria outlined in Section 4.2.3.

4.2.1 Open Fracture Population Eligibility Criteria

The open fracture inclusion criteria are:

1. Patients 18 years of age or older.
2. Open fracture of the appendicular skeleton.
3. Received or will receive definitive fracture treatment with a surgical implant(s) (i.e., internal fixation, external fixation, joint prosthesis, etc.).
4. Open fracture wound management that includes formal surgical debridement within 72 hours of their injury.
5. Will have all planned fracture care surgeries performed by a participating surgeon or delegate.
6. Informed consent obtained.
7. Patient enrolled within 3 weeks of their fracture.

The open fracture exclusion criteria are:

1. Fracture of the hand (distal to radial carpal joint).
2. Patients who did not or will not receive the allocated pre-operative surgical preparation solution due to a medical contraindication.
3. Received previous surgical debridement or management of their fracture at a non-participating hospital or clinic (as applicable).
4. Open fracture managed outside of the participating orthopaedic service (e.g., foot fracture managed by podiatrist).
5. Chronic or acute infection at or near the fracture site at the time of initial fracture surgery.
6. Burns at the fracture site.
7. Incarceration.
8. Expected injury survival of less than 90 days.
9. Terminal illness with expected survival less than 90 days.
10. Currently enrolled in a study that does not permit co-enrollment.
11. Unable to obtain informed consent due to language barriers.
12. Likely problems, in the judgment of study personnel, with maintaining follow-up with the patient.
13. Prior or current enrollment in a PREP-IT trial.
14. Enrolled in the PREPARE closed cohort.
15. Excluded due to sampling strategy.

4.2.2 Closed Fracture Population Eligibility Criteria

The closed fracture inclusion criteria are:

1. Patients 18 years of age or older.
2. Closed fracture of the lower extremity or pelvis.
3. Received or will receive definitive fracture treatment with a surgical implant(s) (i.e., internal fixation, external fixation, joint prosthesis, etc.).
4. Fracture management requires a surgical incision (i.e., for fracture reduction or implant insertion).
5. Will have all planned fracture care surgeries performed by a participating surgeon or delegate.
6. Informed consent obtained.
7. Patient enrolled within 6 weeks of their fracture.

The closed fracture exclusion criteria are:

1. Patients who did not or will not receive the allocated pre-operative surgical preparation solution due to a medical contraindication.
2. Received previous surgical management of their fracture at a non-participating hospital or clinic.
3. Fracture managed outside of the participating orthopaedic service (e.g., foot fracture managed by podiatrist).
4. Chronic or acute infection at or near the fracture site at the time of initial fracture surgery.
5. Burns at the fracture site.
6. Incarceration.
7. Expected injury survival of less than 90 days.
8. Terminal illness with expected survival less than 90 days.
9. Currently enrolled in a study that does not permit co-enrollment.
10. Unable to obtain informed consent due to language barriers.
11. Likely, problems, in the judgment of study personnel, with maintaining follow-up with the patient.
12. Prior or current enrollment in a PREP-IT trial.
13. Enrolled in the PREPARE open cohort.
14. Excluded due to sampling strategy.

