4.4 Randomization Methods

Treatment allocation will be determined using a cluster-randomized crossover trial design. The order of treatment allocation for each orthopaedic practice (cluster) will be randomly assigned using a computer-generated randomization table. Each site will start with the initially allocated study solution and crossover to the other solution for their second recruitment period. Both the open fracture and closed lower extremity and pelvic fracture populations will receive the same treatment allocation and follow the same crossover schedule. The process of alternating treatments will repeat approximately every two months as dictated by the initial randomization. For sites that enroll for more than 1 year, the order of treatment allocation may be reversed after 12 months to ensure equal distribution of each treatment across each calendar month in the study's duration (**Figure 2**). Randomization will be completed by personnel at the CEO Methods Center at the onset of the trial. Personnel from the Methods Center will notify personnel at each participating clinical site of their treatment allocation order. This will allow each participating clinical site to begin preparing for the first run-in period.

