4.5 Blinding

The orthopaedic team (including the study coordinators) cannot be blinded to the treatment allocation as the antiseptic solutions are visually distinguishable and these individuals need to lead the implementation of the cluster-crossover protocol at their clinical site. The Adjudication Committee Members and data analysts will be blinded to the study treatment. All interpretations of study results will initially be done in a blinded manner by developing two interpretations of the results. One interpretation will assume treatment A is iodine povacrylex (0.7% free iodine) in 74% isopropyl alcohol, the other interpretation will assume it is 2% CHG in 70% isopropyl alcohol.

Once the data interpretations for each assumption are finalized, the data will be unblinded and the correct interpretation will be accepted.³⁵

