7.2 Consent

In many cluster randomized comparative effectiveness trials, a waiver of consent is obtained from the IRB of Record. The rationale for the waiver of consent is that all patients will receive treatments that are effective and within standards of care, they will receive one of the study treatments as part of their routine care regardless of study participation, the data collection is minimal and obtained from the patient's medical records, the trial involves no more than minimal risk to the patient, and that the waiver of consent will not adversely affect the rights and welfare of the patient. Most of these concepts apply to the current trial, as the PREPARE trial is comparative effectiveness research where patients will receive one of the preoperative antiseptic skin solutions regardless of their participation in the study. Additionally, patients are never included in the decision-making process for the choice of antiseptic preparation solution, and, in most situations, they are not even aware of which solution is used. However, in contrast to many cluster randomized crossover trials, PREPARE trial personnel will need to contact participants directly to collect baseline and outcome data, as this information cannot be reliably obtained from the patients' medical records. Therefore, study personnel will obtain informed consent from patients prior to data collection. This consent process will allow study participants to be informed about the study rationale and provide consent for ongoing surveillance and data collection.

To increase enrollment and to avoid missing potential study participants, the consent process may take place up to 3 weeks post-fracture for open fracture patients and up to 6 weeks post-fracture for closed fracture patients. Consultation during the study design phase with IRB members and patient advisors confirmed the acceptability of this flexible approach, where consent may be obtained after the intervention. The primary rationale for allowing consent after the intervention is

consistent with the waiver of consent principles outlined above, but in addition, the patient and IRB stakeholders recognized that obtaining consent prior to the patient's first surgery could add undue decision making stress to a patient who is awaiting surgical management of a serious extremity injury; allowing consent after their surgery would likely facilitate an improved consent process.

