The consent process will typically take place in the patient's hospital room or in the outpatient fracture clinic, either before or after the patient has had surgery(ies) to manage their fracture. If the patient is unable to provide informed consent (e.g., due to their injury, language restrictions) within 3 weeks of their open fracture or 6 weeks of their closed fracture, informed consent will be obtained from their proxy. In addition, if a patient has been discharged from hospital prior to being invited to participate in the study, a delegated member of the clinical care team may initiate the consent process by telephone, as approved by the IRB of Record.

To obtain informed consent, delegated study personnel should follow the below procedures:

- Present study information in a manner that is understandable to the potential participant/proxy.
- Discuss the study with the potential participant/proxy and answer any questions he or she asks.
- Allow the potential participant/proxy an opportunity to discuss participation with their family, friends, or family physician, if desired.
- Confirm that the participant/proxy understands the risks and benefits of participating in the study and that their participation is voluntary.
- Complete and obtain signatures for informed consent form and obtain contact information from the participant/proxy.
- Provide/send the participant/proxy with a paper/electronic copy of the signed consent form.

Consent may be obtained electronically or using pen and paper consent forms, as approved by the IRB of Record. If potential participants are contacted by telephone, documenting written informed consent will involve the following procedures:

- The study team confirms the potential participant's interest in learning more about the study and verifies the mailing address or fax number to which the consent form can be sent.
- A blank consent form is mailed or faxed along with a cover letter that introduces the study and explains when the phone conversation will occur. A stamped, self-addressed envelope is provided if standard mail is used so the participant can return the signed consent document to the study team.
- After the potential participant has received the document, a member of the study team calls the participant and walks through the entire document over the phone, answering questions and making notes about the participant's questions. Time and date of the conversation should be recorded.

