64 staged surgical management and that the definitive fracture management surgery involves the final  
65 implantation of the surgical fixation hardware, when it is most susceptible to bacterial  
66 contamination and biofilm development.

67

68 **3.3 Analysis Populations**

69 *Intention-to-Treat*: Our primary analysis will use the intention-to-treat approach and will include  
70 all enrolled patients in the treatment groups to which their cluster was allocated at the time of their  
71 first fracture management surgery.

72

73 *As-Treated*: One of our sensitivity analyses will be performed on an as-treated population (see  
74 Section 5.4). The as-treated population will include participants from the intention-to-treat  
75 population but classified based on the intervention received at their definitive fracture management  
76 surgery. Participants who do not receive one of the two study interventions will be excluded from  
77 this analysis. This approach for defining the as-treated treatment groups is a simpler adaptation of  
78 what was initially proposed in the protocol. This final approach was selected to be consistent with  
79 the classification of adherence outlined above.

80

81

82 **4.0 TRIAL POPULATION**

83 **4.1 Cluster Screening and Eligibility**

84 Prior to commencing the trial, the investigators solicited orthopaedic surgery practices treating  
85 patients with closed fracture(s) of the lower extremity or pelvis in hospitals in the United States  
86 and Canada to participate in the trial. All potential clusters completed a feasibility questionnaire  
87 prior to initiating start-up activities. To be included in the trial, each cluster had to demonstrate: 1)  
88 adequate research personnel infrastructure to manage the study, 2) adequate fracture patient  
89 volume to complete enrolment within the study timeline, 3) a commitment from all surgeons to  
90 adhere to the assigned interventions, and 4) the ability to procure both study interventions. All  
91 hospitals started with a run-in phase of at least 1 month to demonstrate that they could adhere to  
92 the trial protocol prior to commencing the study.

93

94 We will report the number of clusters (orthopaedic practices) screened, included, and excluded in  
95 a flow diagram. The number of clusters excluded by reason has been reported previously. Cluster  
96 randomization allocation will be included in the flow diagram, and adherence with treatment  

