97 allocation during the run-in period by cluster will be summarized using percentages.

98

99 **4.2 Patient Screening and Eligibility**

100 All patients 18 years of age or older who present to a recruiting hospital for treatment of a closed  
101 fracture(s) of the lower extremity or pelvis will be screened by a research staff member for  
102 participation within 6 weeks of their fracture. Eligible patients must receive surgical incision (i.e.,  
103 for fracture reduction or implant insertion), and the closed fracture(s) must be managed definitively  
104 with a surgical implant (e.g., internal fixation, external fixation, joint prosthesis, etc.). Written

105 informed consent is required for study enrollment to permit the clinical follow-up of study  
106 participants. However, our institutional review board did not require informed consent to occur  
107 prior to the study treatment, given the urgent nature of the surgery and the predetermination of the  
108 two commonly used interventions with cluster-crossover design. The patients, treating clinicians,  
109 and research team members at the participating sites are unmasked to the treatment allocation.

110

111 The number of patients screened, included, and excluded will be presented in a flow diagram  
112 (**Figure 1**). The figure will consist of the number of patients who were eligible, ineligible, and  
113 enrolled. In addition, the number of patients excluded by reason will be summarized. We will also  
114 list the number of participants who were enrolled and subsequently deemed ineligible by the  
115 Central Adjudication Committee by treatment group and overall. Participants deemed ineligible  
116 by a central adjudication committee blinded to the treatment will not be included in any analysis,  
117 as per the guidance of Fergusson et al.

118

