64 involves the final implantation of the surgical fixation hardware, when it is most susceptible to  
65 bacterial contamination and biofilm development. 2) Any open fracture surgeries prior to the  
66 definitive fracture management surgery are staged procedures to remove gross contamination,  
67 temporarily stabilize fractures in multi-trauma patients, and minimize evolving soft tissue injuries.

68 Temporally these procedures occur prior to the surgery of interest for the trial's objectives, and if  
69 bacterial contamination had occurred in one of the proceeding procedures, the repeat surgical  
70 debridement and perioperative antibiotics would reduce the likelihood of persistent occult  
71 infection occurring prior to the definitive fracture surgery.

72

73 **3.3 Analysis Populations**

74 *Intention-to-Treat*: Our primary analysis will use the intention-to-treat approach and will include  
75 all enrolled participants in the treatment groups to which their cluster was allocated at the time of  
76 their first fracture management surgery.

77

78 *As-Treated*: One of our sensitivity analyses will be performed on an as-treated population (see  
79 Section 5.4). The as-treated population will include participants from the intention-to-treat  
80 population but classified based on the intervention received at their definitive fracture management  
81 surgery. Participants who do not receive one of the two study interventions will be excluded from  
82 this analysis. This approach for defining the as-treated treatment groups is a simpler adaptation of  
83 what was initially proposed in the protocol. This final approach was selected to be consistent with  
84 the classification of adherence outlined above.

85

86

87 **4.0 TRIAL POPULATION**

88 **4.1 Cluster Screening and Eligibility**

89 Prior to commencing the trial, the investigators solicited orthopaedic surgery practices treating  
90 open fracture patients in hospitals in the United States and Canada to participate in the trial. All  
91 potential clusters completed a feasibility questionnaire prior to initiating start-up activities. To be  
92 included in the trial, each cluster had to demonstrate: 1) adequate research personnel infrastructure  
93 to manage the study, 2) adequate fracture patient volume to complete enrolment within the study  
94 timeline, 3) a commitment from all surgeons to adhere to the assigned interventions, and 4) the  

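### The contraindication exclusion is tied to the solution allocated in that period, so eligibility can differ between arms; any resulting bias is probably very small, and the remedy is cheap.

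*Protocol*

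**What the plan says.** Protocol 4.2.2 (closed fractures, exclusion 1) and 4.2.1 (open fractures, exclusion 2) use the same words: "Patients who did not or will not receive the allocated pre-operative surgical preparation solution due to a medical contraindication". The solution allocated is the one the practice is using in that period. The Randomization Methods section states: "The process of alternating treatments will repeat approximately every two months as dictated by the initial randomization". No other criterion in Protocol 4.2.1 to 4.2.3, and nothing in section 4.2 of either SAP, extends the exclusion to the solution not in use.

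Non-receipt for other reasons is handled differently. Protocol 4.3.1 has potentially eligible patients approached even when they received the wrong solution, and gives preservation of the prognostic balance from randomization as the reason. Protocol 4.6.2 keeps patients whose solution was wrong at one of several surgeries and analyses them as allocated.

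On who applies the rule and when, Protocol 4.5 says "The orthopaedic team (including the study coordinators) cannot be blinded to the treatment allocation", and Protocol 7.2 places the consent discussion "either before or after the patient has had surgery(ies) to manage their fracture".

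Section 3.3 of the closed-fracture SAP defines the intention-to-treat set as "all enrolled patients in the treatment groups to which their cluster was allocated"; the open-fracture SAP has "all enrolled participants in the treatment groups to which their cluster was allocated". On screening exclusions, section 4.2 of each SAP says that "the number of patients excluded by reason will be summarized", with no stated split by allocated solution. Participants found ineligible after enrolment are listed by treatment group (SAP 4.2), and reasons for non-adherence are reported by arm (SAP 3.2).

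**The concern.** Cluster crossover makes the patients who present similar in the two kinds of period. It does not protect against an entry rule that changes with the allocation. Patients who cannot receive iodine povacrylex are removed from iodine periods only, and patients who cannot receive chlorhexidine (CHG) from CHG periods only. If one kind is more common and these patients have a different infection risk, the arms differ before any treatment effect, and a larger sample does not shrink that difference. The exclusion also makes an exception to the principle in Protocol 4.3.1: non-receipt for other reasons stays in, while non-receipt for contraindication drops out after allocation.

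The rule is narrower than it may look in two respects. A contraindicated patient who nevertheless received the allocated solution is not excluded. A contraindication to isopropyl alcohol, the base of both products, acts equally in both arms.

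**Working it through.** **Inputs from the plan.** The minimum sample sizes are 6,280 closed and 1,540 open (Protocol 5.1; SAP 2.3). They follow from Tables 5 and 6: 5,700 × 1.1 = 6,270, rounded up to a multiple of 20, is 6,280; 1,400 × 1.1 = 1,540. This point does not dispute them. Per arm that is 3,140 and 770, or 2,826 and 693 after the planned 10% loss. The CHG-arm SSI risk p is 3.5% closed and 12.5% open, the planned risk ratio is 0.65, and alpha is 0.05 two-sided.

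**Assumed inputs (the documents give none).** c1 is the share of otherwise eligible patients who would not receive iodine because of an iodine-only contraindication. c2 is the same for CHG. k is their SSI risk relative to other patients.

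**Present rule, no true treatment effect.** Risk in each arm, relative to p:

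- Iodine arm: I = [(1 − c1 − c2) + c2·k] / (1 − c1)
- CHG arm: C = [(1 − c1 − c2) + c1·k] / (1 − c2)
- Spurious risk ratio, iodine versus CHG: I / C

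Worked cases:

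- c1 = 1%, c2 = 0, k = 2: I = 1; C = 0.99 + 0.02 = 1.01; ratio 0.990.
- c1 = 3%, c2 = 1%, k = 2: I = 0.98/0.97 = 1.0103; C = 1.02/0.99 = 1.0303; ratio 0.981.
- c1 = 3%, c2 = 0, k = 3: I = 1; C = 0.97 + 0.09 = 1.06; ratio 0.943.

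Type I error uses d = (difference in arm risks)/SE with n per arm after 10% loss, then 1 − Φ(1.96 − d) + Φ(−1.96 − d), ignoring clustering. In the last case, closed: 3.50% versus 3.71%, SE 0.00496, d = 0.42, error 7.08%.

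| c1 | c2 | k | Spurious risk ratio | Type I error, closed / open |
|---|---|---|---|---|
| 1% | 1% | 2 | 1.000 | 5.00% / 5.00% |
| any | any | 1 | 1.000 | 5.00% / 5.00% |
| 1% | 0% | 2 | 0.990 | 5.06% / 5.06% |
| 3% | 1% | 2 | 0.981 | 5.23% / 5.22% |
| 3% | 0% | 3 | 0.943 | 7.08% / 7.01% |
| 0% | 1% | 2 | 1.010 | as for 1% / 0%, arms swapped |
| 1% | 0% | 0.5 | 1.005 | 5.01% / 5.01% |

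In events, the 1% versus 0%, k = 2 case adds 3,140 × 0.035 × 0.01 = 1.1 closed and 770 × 0.125 × 0.01 = 1.0 open infections to the CHG arm. If half of that 1% still received the allocated solution, c1 is effectively 0.5%, C = 0.995 + 0.01 = 1.005, and the ratio is 0.995.

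**Check of the two remedies, no true effect.**

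- Retaining these patients as allocated: both arms contain everyone, so the ratio is 1.000. The price is dilution of a true effect. With c1 = 1%, c2 = 0, k = 2, a true ratio of 0.65, and contraindicated patients in the iodine arm assumed to have the risk they would have had in the CHG arm, the observed ratio is (0.99 × 0.65 + 0.01 × 2) / (0.99 + 0.01 × 2) = 0.6635/1.01 = 0.657.
- Excluding a contraindication to either solution: both arms contain only the uncontraindicated, so the ratio is 1.000 with full ascertainment. If 80% of contraindications to the solution not in use are found, 0.990 becomes 0.998 and 0.943 becomes 0.988. Uneven ascertainment can create bias. At 1% versus 1%, k = 2, where the present rule gives 1.000, finding all the iodine-contraindicated in CHG periods and none of the CHG-contraindicated in iodine periods gives (0.98 + 0.02)/0.99 = 1.010.

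**The case against.** The best defence is that no consequence is demonstrated. Every rate above is assumed, the middle case moves about one infection per population, and 0.943 needs three unfavourable assumptions together: 3%, wholly one-sided, and tripled risk. That stands, and it limits the point to a minor one.

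A second defence is that an either-solution exclusion is not automatically better, because unblinded staff would have to look for contraindications to a product not in use. That also stands, as the 1.010 figure shows. It is why the fix below offers retention under intention-to-treat as an equal option.

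A third is that the SAPs already report much of this. They do so in part. Post-enrolment ineligibility by group and non-adherence reasons by arm both concern enrolled participants. Screening exclusions are promised by reason only. The flow-diagram layouts are not visible in the text available, so a split by allocated solution may already exist.

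Protocol 4.3.1 might be read as overriding the exclusion. It does not, because it covers potentially eligible patients and these are excluded by criterion.

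A reader might go further and infer that the trial is biased towards iodine, or that unblinded staff deciding after surgery used the exclusion selectively. The documents support neither. The sign reverses if CHG contraindication is the more common or if k is below 1, and an opportunity for discretion is not evidence that it was used. The calculation does not model such selection.

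**Conclusion.** The asymmetry is in the wording of both exclusions and needs no figure to establish. Who may enter depends on the allocated solution, contrary to the protocol's own reason for approaching patients who received the wrong one. The size of any bias is unknown: it is zero if the two kinds of non-receipt are equally common with the same k, or if k = 1, and probably very small otherwise. Over the assumed range above, the spurious risk ratio runs from 1.010 down to 0.943, against a planned 0.65, with type I error between 5.0% and about 7%. These figures rest on the assumed c1, c2 and k and on a normal approximation without clustering. The point is minor and worth acting on only because the remedy is cheap.

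**What to change.** Make entry and analysis independent of the allocated solution, in both populations, by one of two routes.

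- **(a)** Enrol these patients and analyse them in their allocated group under intention-to-treat, as the protocol does for other non-receipt (4.3.1, 4.6.2). Nobody is newly excluded; the cost is slight dilution.
- **(b)** Exclude a contraindication to either study solution, whichever is allocated, ascertained in the same way in every period from allergies recorded before surgery. The cost is one line in each criterion and on the screening form, and a little more screening. At 1% versus 0% it newly excludes 0.01 × 3,140 ≈ 31 closed and 0.01 × 770 ≈ 8 open patients, all from the CHG arm. If they were not replaced, power would fall by about 0.24 points (closed) and 0.25 points (open) by a two-proportion approximation.

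Both SAPs are dated February 21, 2023, so recruitment may be complete. If it is:

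1. Split contraindication exclusions at screening by allocated solution in each flow diagram, unless the figure already does so.
2. Give the reason, by group, for ineligibility found after enrolment.
3. Only where contraindication data were recorded (Protocol 4.8.4 does not name them), add a sensitivity analysis removing participants in either arm with a contraindication to either solution. Otherwise state the limitation.

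That costs one split and one reason column per diagram and at most one further model run per analysis. All of this concerns enrolment, analysis and reporting, not what any patient is given.
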